8.3.3 Efficacy Endpoint(s)

Not applicable

8.3.4 Further Endpoints of Interest

Not applicable.

8.4 Analysis Sets

The **safety population** will be defined as all subjects having been included in the present study and have received r-hGH at least once for treatment of short stature due to SGA.

8.5 Description of Statistical Analyses

8.5.1 General Considerations

No statistical significance testing will be performed. The study will contribute to the estimation of the incidence of type 2 diabetes mellitus and the incidence of any malignancy among study participants. Detailed information on statistical analyses and the minimum available data points required to calculate correlations will be specified in the statistical analysis plan (SAP).

8.5.2 Analysis of Primary Safety Endpoints

For primary endpoints, details for each subject of the safety population will be listed and will include at least; time on follow-up, onset date(s) of event(s) and description of event(s).

In parallel with numbers and proportions of subjects experiencing the events, the incidence rate per subject-years of follow-up will be calculated during the 10-year follow-up. The subject-time of follow-up will be defined as the time between the day of last r-hGH treatment and the end of the 10-year period. Furthermore, an analysis of association of the primary endpoints with subject characteristics (e.g., age, sex, blood pressure, BMI, family history) and possible confounding factors of the diseases (e.g., concomitant treatment, medical history, environmental factors) will be conducted. Exploratory analysis will be performed by each brand of r-hGH product if permitted by sample size per brand.

Further details will be provided in the SAP.

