5.3.4 Criteria for Subject Withdrawal

5.3.4.1 Withdrawal from the Study

Subjects will be informed that they have the right to withdraw from the study at any time, without prejudice to their medical care, and they are not obliged to state their reasons.

Withdrawal will be mandatory if the subject is reported to have started an r-hGH therapy during the course of the study.

Subjects who have withdrawn will not be replaced, and the reason for withdrawal will be collected.

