7.4.1.3 Definition of the Adverse Event Reporting Period

The AE reporting period for safety surveillance is defined as the 10-year period after cessation of r-hGH treatment (i.e., during the 10 years after the date of last r-hGH administration).

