8.1 Sample Size

It has been agreed with the Health Authorities to organize an observational study to have followup data on a minimum of 200 subjects born SGA for 10 years after cessation of Saizen® or other r-hGH therapies.

It has been estimated that up to 35% of subjects are likely to be lost or will drop out during the 10-year study duration (which can be due to withdrawal of consent, lost to follow-up, or death). Therefore, it was decided to recruit approximately 300 subjects in the SALTO study to have the 200 subjects for the final analysis at 10 years of follow-up. The sample size of 300 subjects represents 150% of the 200 subjects completing the study, as requested by the Health Authorities.

While recruitment is still open, the Sponsor will closely monitor the subject dropout rate to determine the need to recruit additional subjects. If the attrition rate is anticipated to be greater than 35%, additional subjects may be recruited to maximize the probability that 200 patients will have completed the study.

Figure 2 Determination of planned sample size.

^{*}Discontinuation includes: Lost to FU, protocol deviation, non-compliance, AEs, patient decision and other reasons.

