8.7 Imputation of missing data

Imputation of missing data will be performed for the analyses performed at the 5- and 10-year time points. An example is given as follows:

- If a subject experienced an event after 3 years and then dropped-out at 4 years, then this subject will be incorporated into the 5- and 10-year analyses as having had the event.
- If a subject dropped-out at a given time *t* without having experienced an event, this subject will not be included in subsequent analyses (after time t).

This imputation of missing data will not be applied to analyses of "subject-years".

9 Ethical and Regulatory Aspects

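### The subject-time definition in Section 8.5.2 has no stop at loss, withdrawal, death or diagnosis; taken literally, it understates both primary incidence rates by roughly 9–19% at 35% loss

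*Protocol*

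**What the plan says.** Section 8.5.2 reports numbers and proportions of subjects with type 2 diabetes or any malignancy and, alongside them, a rate: "the incidence rate per subject-years of follow-up will be calculated during the 10-year follow-up". It then defines the denominator: "The subject-time of follow-up will be defined as the time between the day of last r-hGH treatment and the end of the 10-year period". Section 7.4.1.3 places the reporting period "during the 10 years after the date of last r-hGH administration", so the window has the same length for every subject.

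The protocol expects many subjects to leave before it closes. Section 8.1 says: "It has been estimated that up to 35% of subjects are likely to be lost or will drop out during the 10-year study duration", and gives the reasons: "which can be due to withdrawal of consent, lost to follow-up, or death". Section 5.3.4.1 adds another: "Withdrawal will be mandatory if the subject is reported to have started an r-hGH therapy during the course of the study". The safety population in Section 8.4 is all included subjects, not only completers.

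Section 8.7 has a drop-out rule for the 5- and 10-year analyses. A subject with an event before leaving is carried forward as having had it; a subject who leaves event-free is dropped from later analyses. The section then excludes subject-years from this rule and offers no replacement.

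**The concern.** An incidence rate needs a numerator and a denominator that cover the same observation time. Here the numerator effectively stops when a subject leaves, because later diagnoses will mostly go unreported. The denominator as defined runs on to year 10. It also runs on after death and after first diagnosis, when the subject is no longer at risk of a first event.

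The error always points the same way: the rates look lower than they are. The study is a post-approval safety commitment (Section 3) with no control group (Section 5.1) and no significance testing (Section 8.5.1), so these estimates are the main result. A systematic shift towards reassurance matters more here than it would in a between-group comparison, where it might partly cancel.

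**Working it through.** **The plan's own figure.** 200 completers with 35% loss need 200 / (1 − 0.35) = 307.7, so 308. The protocol states about 300, which is 200 × 1.5 and leaves 300 × 0.65 = 195 completers at the full 35%. That is close enough and is not at issue. The protocol states no subject-years total or event rate to reproduce.

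**Inputs.** N = 300 and d = 0.35 (Section 8.1); window 10 years (Sections 7.4.1.3 and 8.5.2); enrolment possible from the day after the last dose up to 5 years later (Section 5.1). The mean time of loss, m years after the last dose, is not given and is assumed below.

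**Formulas.**
- Literal subject-years = N × 10 = 3,000.
- Observed subject-years = N × [(1 − d) × 10 + d × m].
- Literal rate / observed-time rate = observed / literal = 1 − d × (10 − m) / 10.

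Nobody can be lost before enrolling, so later entry pushes m later. With loss uniform from entry to year 10, m is the midpoint of mean entry time and 10. For constant hazard from the last dose, h = −ln(0.65)/10 = 0.0431 per year and observed time = 300 × 0.35 / h.

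| Assumed entry and loss | m | Observed subject-years | Rate ratio | Understated by |
|---|---|---|---|---|
| All enrol at last dose, constant hazard | 4.64 | 2,437 | 0.812 | 18.8% |
| All enrol at last dose, uniform loss | 5 | 2,475 | 0.825 | 17.5% |
| Entry uniform over years 0–5, uniform loss after entry | 6.25 | 2,606 | 0.869 | 13.1% |
| All enrol at year 5, uniform loss after entry | 7.5 | 2,737.5 | 0.9125 | 8.75% |

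For the third row: 300 × (6.5 + 0.35 × 6.25) = 2,606, and 0.35 × 3.75 / 10 = 13.1%.

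**Lower loss.** The shortfall is proportional to d. At half the stated ceiling (17.5%), the third row becomes 0.175 × 3.75 / 10 = 6.6%.

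**Time after diagnosis.** With no loss and a constant event rate λ, the ratio is (1 − e^(−10λ)) / (10λ). At an assumed 1 per 1,000 subject-years it is 0.995 (0.5% too low); at 10 per 1,000 it is 0.952 (4.8% too low). For rare events, nearly all the bias comes from loss and death.

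**The case against.** The best defence is that the sentence only fixes the origin (last dose rather than consent) and the administrative end. Several places fit that reading. Section 8.5.2 lists time on follow-up per subject, which would be pointless if it were always 10 years. Sections 5.1 and 7.1 treat 10 years as a maximum. Section 5.3.6 lets a subject finish by early termination. Section 8.7's exemption may mean that leavers stay in and contribute their observed time. Section 8.5.2 also defers details to the SAP. This is a plausible account of intent, but it does not correct an explicit definition: a SAP that censored individually would have to depart from the protocol's sentence.

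Four stronger readings are tempting and are not supported:
- A reader might infer that Section 8.7 confirms a fixed 10 years. It is ambiguous and confirms neither reading.
- A reader might take 17.5–19% as the size of the bias. That assumes loss can begin at the last dose for everyone, while enrolment may come up to 5 years later; 35% is also a ceiling.
- A reader might infer that 10 years per subject would be counted at the 5-year interim. Section 8.6 sets those analyses at 5 years, so that is implausible. What stands is that the definition does not fit the interim and needs its own end point there.
- A reader might assume the censoring dates are all in hand. Table 1 lists no last-contact or last-known-status date.

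It is also fair that random error would exceed the bias. About 12 events, as with a true rate near 5 per 1,000, give an exact 95% interval from roughly 48% below to 75% above the estimate. The per-subject listing would let the rate be recomputed. But the bias runs in one direction, and the interval would be built around the wrong value.

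**Conclusion.** The point stands as a wrongly stated rule, not as a missing detail. Followed as written, Section 8.5.2 puts unobserved time into the denominator of both primary rates and biases them downwards. At 35% loss the understatement is roughly 9–19% across the entry and loss patterns tabulated, and it falls in proportion as loss falls. These figures rest on assumed timing that the protocol does not give, and on events after leaving not being captured. Time after diagnosis is a minor contributor. It is not established that 3,000 subject-years will in fact be counted, since the authors may intend observed time; the protocol should say so.

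**What to change.** Replace the defining sentence in Section 8.5.2 with wording to this effect: for each primary endpoint, subject-time runs from the last r-hGH dose to the earliest of first diagnosis of that endpoint, death, withdrawal from the study (including the mandatory withdrawal in Section 5.3.4.1), last contact at which event status was known, the analysis cut-off (5 years after the last dose for the interim), and 10 years after the last dose. In Section 8.7, state that subject-years follow this definition, and carry it into the SAP.

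The text change is small. Onset dates are already recorded (Sections 7.4.1.2 and 8.5.2). The date of last contact with known status may need a new eCRF field, because Section 9.3 keeps the contact and clinical databases unconnected. The yearly calls in Section 7.1 provide a natural occasion to record it.

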8.5.3 Analysis of Secondary Safety Endpoint(s)

All secondary endpoints will be analysed using appropriate statistics. For quantitative variables, statistics are the number of non-missing values (N), number of missing values, mean, standard deviation (SD), minimum (Min), first quartile (Q1), median, third quartile (Q3) and maximum (Max). For qualitative variables, statistics within categories are number of non-missing values (N), number of missing values and percentages of subjects.

Further details will be provided in the SAP.

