	 Exclusion criteria Patients unwilling and/or parents/guardians who are not capable of ensuring compliance with the study protocol. Patients enrolled in an interventional trial Patients enrolled in an observational trial of a similar nature to the SALTO study, where the protocol includes reporting of incidence of type 2 diabetes mellitus and/or malignancies after cessation of r-hGH therapy. 		
Investigational Medicinal Product (s): dose/mode of administration/dosing schedule	Not Applicable (observational study).		
Reference therapy(ies): dose/mode of administration/ dosing schedule	None (post-treatment observational study).		
Planned treatment duration per subject	None (post-treatment observational study).		
Primary endpoint(s)	Incidence of type 2 diabetes mellitus		
	Incidence of any malignancy		
Secondary endpoint(s)	• Incidence of metabolic syndrome and changes in glucose metabolism parameters (glycaemia parameters – fasting plasma glucose and postprandial glucose, fasting plasma insulin levels, HbA1c, 2-hour oral glucose tolerance test (OGTT) results, blood pressure, lipid parameters).		
	 Parameters related to malignancies (typology, size and location as applicable, grading, severity, treatment, outcome) 		
	Correlation of type 2 diabetes mellitus and/or malignancy will be established against blood pressure, body mass index, lipid parameters, medical history and familial inheritance		
Statistical methods (includes sample size calculation)	It has been agreed with the Health Authorities to organize an observational study to follow-up 200 short children born SGA for 10 years after cessation of treatment with Saizen® or other r-hGH products. In order to compensate for an estimated 35% loss to follow-up, we will recruit 150% of the requested target number of 200 subjects. Hence, a sample size of approximately 300 subjects is targeted for study enrolment.		

Numbers and proportions of subjects having the events (type 2 diabetes mellitus and any malignancy), will be computed, as will the incidence rate per subject-years of follow-up during the 10-year follow-up. Analysis of correlations of the primary endpoints with subject characteristics (e.g., age, blood pressure, Body Mass Index [BMI], family history) and possible confounding factors of the diseases (e.g., concomitant treatment, environmental factors) will be conducted. Exploratory analysis will be performed for each brand of r-hGH product if permitted by sample size per brand.

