2. Malignancy risk: low birth weight has not been shown to be associated with increased risk of cancer in general, with the possible exceptions of testicular and renal cancer (4). A number of studies were retrieved in the published literature discussing the occurrence and/or recurrence of cancer or neoplasm during GH therapy. In one medium-sized and two large studies, GH therapy was not associated with an increase in the incidence of a first cancer compared to the general population.

However, GH treatment during childhood of survivors of cancer treatment has also been shown to increase slightly the relative risk of a second neoplasm (15), (16). Growth hormone therapy studied in two populations of cancer survivors, one with a control group, found an elevated risk of developing a secondary solid tumour in childhood cancer survivors treated with GH compared with non-treated survivors for one and a statistically significant raised frequency of colon cancer mortality after pituitary-derived GH treatment in another.

This observation is however disputed, given that other surveillance studies revealed no increase in observed cancer risk (17). The above results are based on a very small number of cases and may therefore require cautious interpretation.

There have been rare reports of brain tumours (de novo/recurrence) or leukaemia and extra-cranial solid tumour in subjects treated with Saizen® in the post-marketing surveillance period. From the currently available data, there is no evidence suggesting that Saizen® may increase the risk of cancers in treated subjects. It must also be noted that with an overall increase in subject-years of exposure, adverse events (AEs) which are related to commonly experienced medical conditions (as seen in the general population) tend to also be reported in the population treated with GH. However, no increase of reporting rates concerning neoplasms, both de novo and recurrence, was identified cumulatively since first marketing authorization of Saizen®.

4 Study Objectives

Primary objective of the study:

To assess the long-term safety of Saizen® or other r-hGH treatment for 10 years after cessation
of treatment, in terms of occurrence of type 2 diabetes mellitus and malignancies, in a minimum
of 200 subjects born SGA who received Saizen® or other r-hGH products for the treatment of
short stature

Secondary objectives of the study:

- To assess occurrence of metabolic syndrome
- To assess glucose metabolism parameters

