8.3.2 Secondary Endpoints

- Metabolic syndrome and/or changes in glucose metabolism parameters as per
 - Glycaemia parameters, fasting plasma glucose and postprandial glucose, and/or fasting plasma insulin levels
 - HbA1c
 - 2-hour OGTT results
 - Blood pressure
 - Lipid parameters.
- Malignancies (including typology, size and location, as applicable, grading, severity, treatment, outcome)
- Correlation of type 2 diabetes mellitus and/or malignancies will be established against

- Blood pressure (BP)
- Body Mass Index (BMI)
- Lipid parameters
- Medical history
- · Familial inheritance

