8.6 Interim Analysis

All the analyses described above (primary and secondary safety endpoints) for the 10-year final analysis will also be performed at 5 years after cessation of r-hGH treatment.

The 5-year interim analysis will be performed when 200 subjects enrolled in the study will have completed the 5-year study period after discontinuation of r-hGH treatment, and will include the available clinical data from 5 years after discontinuation of r-hGH treatment.

Further details will be provided in the SAP.

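### Incidence of metabolic syndrome is a secondary endpoint, but the only summary named for it is a percentage, which under 8.6 and 8.7 overstates the 10-year risk about 1.2-fold at 35% loss

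*Protocol*

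**What the plan says.** The wording of the endpoint varies. The synopsis has "Incidence of metabolic syndrome and changes in glucose metabolism parameters". The first secondary objective (synopsis and section 4) is "To assess occurrence of metabolic syndrome". Section 8.3.2 lists "Metabolic syndrome and/or changes in glucose metabolism parameters as per" a set of parameters, and does not mention incidence.

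For the two primary endpoints, section 8.5.2 plans numbers and proportions, and adds that "the incidence rate per subject-years of follow-up will be calculated during the 10-year follow-up".

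For the secondary endpoints, section 8.5.3 begins "All secondary endpoints will be analysed using appropriate statistics", then lists the statistics. The relevant sentence is "For qualitative variables, statistics within categories are number of non-missing values (N), number of missing values and percentages of subjects". It ends "Further details will be provided in the SAP". It names no rate, time base or at-risk set.

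Section 8.6 states: "All the analyses described above (primary and secondary safety endpoints) for the 10-year final analysis will also be performed at 5 years". Section 8.7 then gives, by way of example, the rule for subjects who leave. A subject with an event before leaving counts as an event at both 5 and 10 years. A subject who leaves without an event is excluded from analyses after that time. The rule is expressly not applied to subject-years analyses. Section 8.1 allows for up to 35% loss over the 10 years.

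**The concern.** An incidence endpoint in a cohort with unequal follow-up needs a summary that accounts for time at risk. The protocol provides one for two of its incidence endpoints and not for the third, which is the subject of the first secondary objective.

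The percentage that remains is not neutral. Under 8.7 the numerator keeps everyone who had an event before leaving, while the denominator loses everyone who left without one. The proportion is therefore pushed upward, and more so the heavier the loss. A reader who sets it beside an outside figure for 10-year risk would see an excess created by the drop-out rule.

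A second gap is definitional. Section 8.5.3 does not say whether the year-5 or year-10 percentage counts subjects with a first onset by then or subjects who meet the criteria at that time. These are different quantities if the condition can resolve.

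**Working it through.** **Inputs from the protocol.** Loss of up to 35% over 10 years, about 300 enrolled and 200 wanted at 10 years (8.1); the 5- and 10-year analyses cover secondary endpoints (8.6); events kept and event-free drop-outs removed (8.7).

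**The protocol's own figure.** 150% × 200 = 300, as stated. Dividing by the retained fraction gives 200 / 0.65 = 308, close to the approximate 300. At exactly 35% loss, 300 × 0.65 = 195 subjects remain. Enrolment is not in dispute; 35% is used only as the loss input.

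**Assumptions.** The protocol gives no rate for metabolic syndrome, so true 10-year risks R of 2%, 5%, 10% and 20% are assumed, with constant hazards, loss independent of onset, and all subjects free of the condition at the start.

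**Formulas.**
- Loss hazard: c = −ln(0.65)/10 = 0.0431 per year.
- Onset hazard: h = −ln(1 − R)/10.
- Proportion with an observed event: E = h/(h + c) × [1 − exp(−10(h + c))].
- Proportion completing 10 years event-free: F = exp(−10(h + c)) = (1 − R) × 0.65.
- Percentage under 8.7: E/(E + F).
- Observed years per subject: T = [1 − exp(−10(h + c))]/(h + c). Rate = E/T.

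**For R = 10%.** h = 0.0105; F = 0.90 × 0.65 = 0.585; E = 0.0816. The 8.7 percentage is 0.0816/(0.0816 + 0.585) = 12.2%. With 300 enrolled, that is about 24.5 events over a denominator of about 200. E/T = 10.5 per 1000 subject-years, the assumed rate.

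| Assumed true 10-year risk | Percentage under 8.7 | Ratio to truth | Events per 1000 observed subject-years (equals assumed rate) |
|---|---|---|---|
| 2% | 2.5% | 1.2 | 2.0 |
| 5% | 6.2% | 1.2 | 5.1 |
| 10% | 12.2% | 1.2 | 10.5 |
| 20% | 24.0% | 1.2 | 22.3 |

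**Would extending 8.5.2 to this endpoint be enough?** Not if read literally. Section 8.5.2 runs subject-time from the last r-hGH treatment to the end of the 10-year period. Giving every subject 10 years yields 0.0816/10 = 8.2 per 1000 instead of 10.5. The time has to be observed time.

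**The case against.** The strongest reply is that this is ordinary deferral. Section 8.5.3 speaks of appropriate statistics, does not say that its list is exhaustive, and sends details to the SAP, so a rate is not ruled out. That is fair, and it lowers the priority. It does not dispose of the point: 8.5.2 also defers details to the SAP yet commits to a rate, and the percentage that 8.5.3 does name falls under a drop-out rule that distorts it.

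Three stronger readings might be inferred, and the documents do not support them.
- *That the analysis does not estimate incidence at all.* Table 1 collects occurrence of metabolic syndrome at any time over the 10 years, the condition falls under the adverse events of interest (7.1, 7.4.1.1), and 7.4.1.2 asks for onset dates. A percentage of subjects with onset during follow-up is an incidence proportion, though a biased one here.
- *That the denominator is fixed as subjects with non-missing values.* Section 8.5.3 lists the non-missing count, the missing count and percentages, and does not say what the percentage is taken over.
- *That recovery makes the figure too low.* With an assumed remission of 5% to 20% per year, a true 10% would appear as 7.9% to 4.4% at year 10. But the protocol gives no remission rate and does not say that status at year 10 is what is scored, and carrying events forward under 8.7 points the other way. Likewise, taking events over all enrolled would give 8.2%, but 8.7 does not use that denominator.

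The objection that a rate is no cure for sparse data also stands in part. No visits or tests are scheduled, so subject-years count unmeasured time as event-free. That is why the number assessable must be shown beside the rate.

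**Conclusion.** The point holds in limited form. The synopsis promises an incidence; 8.5.3 names only a percentage and leaves its meaning and denominator open; and 8.7, applied through 8.6, biases that percentage upward by about 1.2 times at 35% loss. The size rests on constant hazards, independent loss, the full 35% being lost, and 8.7 applying to secondary endpoints, as 8.6 indicates on its face. The true risks are illustrative.

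Priority is low to moderate. The endpoint is secondary, section 8.5.1 excludes significance testing, and the SAP is not at hand. No conclusion on the primary endpoints depends on it.

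**What to change.** In 8.5.3, add for metabolic syndrome:
- the number of subjects with a first occurrence;
- the incidence rate per observed subject-years, counted from the last r-hGH dose to first occurrence or last known status, and not to the end of the 10-year period for everyone;
- restriction of both to subjects without the condition at baseline;
- beside them, the number of subjects with enough data to be assessed.

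Label any year-5 or year-10 percentage that reflects current status as prevalence, and align the endpoint wording in the synopsis and 8.3.2. Since 8.7 already exempts subject-years analyses from its drop-out rule, no change to 8.7 is needed for the rate.

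The cost is a few sentences and one extra table. Table 1 and the adverse event reports already provide for occurrence and onset dates where available. The downside is that onset dates and event-free time are only as reliable as routine care makes them, and the report should say so.
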